This will be a 6-week, open-label, randomized clinical trial study to compare efficacy and tolerability of the natural treatments omega-3 fatty acids, inositol, and NAC in the treatment of mood dysregulation in children and adolescents with NVLD/ASD. Subjects will include youth ages 5-17 years with a non-verbal learning disability (NVLD) or autism spectrum disorder (ASD) and current symptoms of emotional dysregulation. We will enroll 60 subjects to allow for the randomization of 30 subject into each treatment arm.

The full inclusion and exclusion criteria are included below:

A. Inclusion Criteria:

1. Male or female subjects, 5-17 years of age.
2. A previous established diagnosis of non-verbal learning disability (NVLD) or DSM-V Autism Spectrum Disorder and/ or combined T-scores on the Child Behavior Checklist \geq 195 on the Withdrawn + Social Problems + Thought Problems subscales.

3. Current symptoms of emotional dysregulation as indicated by combined T-scores on the Child Behavior Checklist ≥ 180 on the Anxiety/Depression + Aggression + Attention subscales.
4. Subjects and their caregivers must be English-speaking and have a level of understanding sufficient to communicate intelligently with the investigator and study coordinator, and to cooperate with all tests and examinations required by the protocol.
5. Subjects and their caregivers must be willing and able to comply with all study procedures.
6. Each subject and his/her authorized legal representative must understand the nature of the study. The subject's authorized legal representative must sign an informed consent document and the subject must sign an informed assent document.
7. Subject must be able to swallow pills.
8. Subject must have access to a computer with a camera, speaker, microphone, and internet connection.
9. Subjects must be willing to refrain from treatment changes during the study protocol.

B. Exclusion Criteria:

1. Investigator and his/her immediate family; defined as the investigator's spouse, parent, child, grandparent, or grandchild.
2. Serious or unstable illness including hepatic, renal, gastroenterological, respiratory, cardiovascular (including ischemic heart disease), endocrinologic, neurologic, immunologic, or hematologic disease.
3. History of bleeding diathesis, including those with von Willebrand disease.
4. Uncorrected hypothyroidism or hyperthyroidism.

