Interested parents/guardians will first complete a phone screen with the study coordinator or a research assistant. If the child meets eligibility criteria based on the phone screen, the parent/guardian will be asked to complete the Child Behavior Checklist (CBCL) via RedCap, a secure online data capture system. The parent/guardian will be provided with an online consent statement and asked to indicate their agreements to participate in the online questionnaire portion of the study before they are brought the CBCL.

If a parent/guardian has completed pre-screening procedures for another research study or the clinic in our department within the past 3 months, they will not be asked to complete that procedure again, and the data collected previously will be used for pre-screening for this protocol.

Subjects deemed to be eligible following the phone screen and completion of the CBCL will either be scheduled for an in-person visit at our office or, during the COVID-19 pandemic, to speak with a study clinician via phone to obtain informed consent prior to completing further screening and baseline study procedures via virtual visit. Informed consent will be obtained from all subjects and their legal guardian at the initial in-person visit or, during the COVID-19 pandemic, during a phone call with a study clinician. The subject's legal guardian will then answer questionnaires regarding current medications and demographic details. They will also complete the BRIEF, SRS, P-YMRS, and CDI questionnaires. A study clinician will complete the Columbia Suicide Severity Rating Scale (C-SSRS) to assess past and current suicidality and self-harmful behaviors; conduct an observational mental status exam; record baseline severity scores of Clinical Global Impression (CGI) for mania, depression, and overall bipolar disorder; and will review current medications and recommend any medication taper. A trained member of study staff will obtain and record height and weight for all subjects. A urine pregnancy test will be conducted for all female subjects who have reached menstruation. If the test is positive, the subject will not be able to participate in the study and she will be informed of the results, along with her parent/guardian if she agrees. Even if she does not agree, the study doctor may still decide, based on the subject's age, maturity, or medical condition, to inform the parent/guardian.

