call with the subject and their parent(s)/guardian on the same day as the tele-visit with the study clinician in order to complete the following procedures. Parents/guardians will be asked to self-report height and weight. It will be noted that these measurements were provided by a parent/guardian report rather than study staff measurement. For any female subjects who have begun menstruation, a pregnancy test will be ordered using study funds and sent directly to the subject's home address. The test will be ordered in advance to ensure delivery before the week 99/0 tele-visit. The study coordinator will review the procedure for completing the urine pregnancy test while on the phone and have the subject complete the test while remaining on the line. The subject/subject's parent or guardian will verbally report the result to the study coordinator, and will also send visual confirmation (i.e. a photo of the test with results send via secure email) prior to beginning the study treatment. Finally, the study coordinator will send an email link to the parent(s)/guardians to complete a battery of assessments/rating scales via REDCap. All typically completed parent assessments/rating scales can safely and effectively be completed remotely. These assessments/rating scales are already approved to be completed via email link to REDCap for the week 1-6 tele-visits.

At each following weekly tele-visit, parents will indicate adherence to the study treatment, list any new concomitant medications, and complete questionnaires regarding symptoms of emotional dysregulation, mania, and depression. A study clinician will also complete the C-SSRS to monitor suicidality and self-harmful behaviors, record CGI (Severity and Improvement) scales for mania, depression, and overall bipolar disorder, record any side effects or adverse events, and review and confirm parent-reported information.

At endpoint, parents will report current weight and complete the BRIEF and SRS questionnaires in addition to the weekly questionnaires.

For studies involving treatment or diagnosis, provide information about standard of care at Partners (e.g., BWH, MGH) and indicate how the study procedures differ from standard care. Provide information on available alternative treatments, procedures, or methods of diagnosis.

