Poor response to treatment, leading to drop from the study, will be measures by a CGI-bipolar score that is 2 points higher (more severe) than baseline for more than 2 consecutive weeks or a P-YMRS score that is 30% higher than baseline for more than 2 consecutive weeks only if the P-YMRS is in a clinically significant range of >15. If a subject should score a 4 or higher on the C-SSRS, he or she will be dropped from the study. The study clinician will assess the level of risk and take appropriate actions, including an immediate referral to emergency services.

In addition, drop from the study will occur at clinician discretion for worsening of clinical course, non-compliance with treatment, or inability to tolerate study treatment.

Subjects who fail to keep study appointments or are non-complaint (less than 70% compliance for 2 weeks or longer) may be dropped from the study. If a subject becomes pregnant or is found to be abusing substances during the study, he or she will be dropped from the study. These study subjects will be given a referral for local treatment.

FORESEEABLE RISKS AND DISCOMFORTS

Provide a brief description of any foreseeable risks and discomforts to subjects. Include those related to drugs/devices/procedures being studied and/or administered/performed solely for research purposes. In addition, include psychosocial risks, and risks related to privacy and confidentiality. When applicable, describe risks to a developing fetus or nursing infant.

Potential side effects are few and will be monitored for throughout the research study. Consent forms will clearly list potential treatment side effects. Since they are natural products, it appears that omega-3 fatty acids, inositol, and NAC have a low potential for unwanted side effects or negative effects on the child's growth and development. It should also be noted that no important toxic effects have been reported in previous use in humans and animals.

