Natural Treatments for the Management of Emotional Dysregulation in Youth With Non-verbal Learning Disability (NVLD) and/or Autism Spectrum Disorders (ASD)

NCT03757585

April 23, 2025

Statistical Methods

Participants were included in the analysis based on a modified intent to treat analysis plan with the criterion that participants had to be exposed to the study medications for ?2 weeks. Baseline clinical characteristics were examined using Pearson's chi-squared test for dichotomous measures and truncated Poisson regression models for continuous measures (CBCL-AAA and CBCL-AT: lower level [II] of truncation=150, upper level [ul] of truncation=270; SRS: ll=30, ul=90; BRIEF: ll=30, ul=100; YMRS: ul=60; CDI: ul=40). Primary efficacy measures of mania and depression, as well as secondary measures of autism symptoms and executive functioning, were analyzed using mixed-effects Poisson regression models predict the outcome measure of interest from the study group, study week (continuous), and the study group-by-study week interaction, which is the primary effect of interest. Secondary efficacy measures of mania and depression assessed at endpoint were examined using logistic regression models predicting the outcome of interest from the study group. Adverse events (AEs) were analyzed using a Poisson regression model for AE counts and Fisher's exact tests for AE prevalence. All analyses were two-tailed with an alpha level of 0.05 and conducted using Stata (Version 18.1) (StataCorp, 2023).

We also examined the moderating effect of 1) the CBCL Autistic Traits (AT) profile defined by a combined T-score ?195 on the CBCL Withdrawn/Depressed, Social Problems, and Thought Problems scales, and 2) the CBCL-Bipolar (BP) profile defined by a combined T-score ?210 on the CBCL Aggressive Behavior, Attention Problems, and Anxious/Depressed scales. To examine these moderating effects, we added a 3-way interaction term between study group, study visit, and CBCL profile group to each of the models for the primary and secondary outcomes of interest. The moderating effects of the CBCL-AT and CBCL-BP profiles were examined separately.

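### The endpoint logistic models for the secondary mania and depression measures leave out the matching baseline score; the unadjusted test is valid overall, but it ignores baseline information already collected

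*SAP*

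**What the plan says.** In the SAP, Statistical Methods, the secondary mania and depression measures at endpoint were "examined using logistic regression models predicting the outcome of interest from the study group". Study group is the only predictor named, and the protocol adds none.

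The matching baseline scores exist. At the screening/baseline visit (Protocol, Research Design and Methods) the guardian's tasks are described thus: "They will also complete the BRIEF, SRS, P-YMRS, and CDI questionnaires". The clinician is to "record baseline severity scores of Clinical Global Impression (CGI) for mania, depression, and overall bipolar disorder". The SAP's list of baseline measures compared between arms includes "YMRS: ul=60; CDI: ul=40", so YMRS and CDI are in the analysis dataset as baseline variables.

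On size, the protocol states: "We will enroll 60 subjects to allow for the randomization of 30 subject into each treatment arm".

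Neither document says how the binary endpoint measures are defined. At the weekly visits the clinician is to "record CGI (Severity and Improvement) scales for mania, depression, and overall bipolar disorder", so a CGI-based measure is possible, either as a severity cutoff or as an improvement rating. The withdrawal rule uses a P-YMRS score "30% higher than baseline for more than 2 consecutive weeks only if the P-YMRS is in a clinically significant range of >15". It combines a relative change with an absolute level, but it is not an endpoint definition.

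**The concern.** A child's score at week 6 usually depends in part on the score at entry. A logistic model with treatment group alone treats that predictable variation as noise. Two things may follow. The test may have less power than the data allow. And if the arms happen to differ in baseline severity, the endpoint comparison carries that difference forward uncorrected.

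With 30 per arm, moderate chance imbalance is not rare. At stake is how far a secondary finding on mania or depression, positive or negative, can be read as a treatment difference rather than a difference in starting severity.

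**Working it through.** The documents give no effect size, SD, response rate, baseline-endpoint correlation or power figure, so there is nothing of the plan's own to reproduce. From the documents: 30 per arm, two-sided alpha 0.05, group-only model. Everything else below is an assumption.

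**1. How often the arms differ at baseline.** The difference in means of a standardised score has SD sqrt(2/30) = 0.258.
- P(0.3 SD or more, either direction) = 2 × (1 − Φ(0.3/0.258)) = 24.5%.
- P(0.5 SD or more) = 2 × (1 − Φ(0.5/0.258)) = 5.3%.

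**2. What an imbalance does to a cutoff outcome.** Take baseline x ~ N(0,1) and endpoint y = r·x − shift·group + sqrt(1 − r²)·e, with success if y < k = Φ⁻¹(0.4). With no treatment effect and an imbalance of 0.3 SD, the gap in success rates is Φ(k + 0.15r) − Φ(k − 0.15r). This is 3.5, 5.8 and 8.1 points at r = 0.3, 0.5 and 0.7.

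**3. Power for a cutoff outcome.** The models compared are logit P = a + b·group and logit P = a + b·group + c·x, with a likelihood-ratio test of b (20,000 simulated trials per cell for the raw figures). Shifts of 0.3, 0.5 and 0.74 SD correspond to 40% v 52, 60 and 69% success. Entries are unadjusted → adjusted power (%), then the gain in points when each test uses its own simulated 5% critical value.

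| Shift | r = 0.3 | r = 0.5 | r = 0.7 |
|---|---|---|---|
| 0.3 SD | 15.2 → 16.4; +0.1 | 15.5 → 17.9; +0.5 | 15.6 → 21.5; +3.2 |
| 0.5 SD | 34.5 → 36.3; +0.4 | 33.8 → 39.7; +2.2 | 34.4 → 47.6; +9.1 |
| 0.74 SD | 63.1 → 65.4; +0.6 | 61.7 → 69.2; +6.4 | 62.7 → 78.8; +14.4 |

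The raw gains are partly a size effect: overall type I error is about 5.1% unadjusted and 5.4 to 5.7% adjusted (up to 6.0% in a repeat run). The size-matched gains are the fair comparison. They move by a point or two between runs; a repeat gave about 0 to 2 at r = 0.3 and about 4 to 13 at r = 0.7.

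**4. Power for a percent-reduction outcome.** Baseline 25 + 7x, endpoint 18 + 7y, success if the endpoint is at most 70% of baseline. Raw gains in points at shifts 0.3, 0.5 and 0.74 SD:
- r = 0.3: +1.3, +3.2, +4.7
- r = 0.5: +0.9, +1.4, +1.2
- r = 0.7: +0.1, +0.2, −0.5

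**5. Smaller arms.** At an assumed 25 per arm, raw gains run from −1.3 to +13.7 for the cutoff (all negative at r = 0.3) and from −1.7 to +1.7 for the percent reduction. Here the unadjusted test is the more liberal one (type I error 6.0 to 6.4% v 5.6 to 5.9%), which accounts for part of the loss.

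**6. Type I error given imbalance, cutoff outcome.** Across all null trials with an imbalance of 0.3 SD or more, at r = 0.3, 0.5 and 0.7:
- unadjusted: 6.8, 8.6 and 11.5% (repeat run 6.1, 8.9 and 11.6%);
- adjusted: 6.0, 5.6 and 6.2% (repeat run 5.3, 5.9 and 5.7%).

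At exactly 0.3 SD the unadjusted error is 5.3, 5.5 and 5.7%; the excess comes from the larger imbalances. The other trials offset it. At r = 0.7 their error must be about (5.1 − 0.245 × 11.5)/0.755 = 3.0%, which is how the overall rate stays near 5%. For a percent-reduction outcome with 0.3 SD or more, the unadjusted error was 6.9, 5.6 and 5.0%; with the imbalance fixed at 0.5 SD it was 8.4, 7.0 and 5.1%.

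**7. Precision.** For the cutoff at 0.74 SD, the SE of the log-odds ratio rises from 0.55 to 0.58, 0.63 and 0.74 with adjustment, because the adjusted odds ratio is a different, conditional quantity. On the risk-difference scale the sampling SD falls to about 0.98, 0.93 and 0.83 to 0.84 of the unadjusted value (percent reduction: 0.96 to 1.01).

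**The case against.** The strongest reply is that an unadjusted comparison in a randomised trial is legitimate, these are secondary outcomes, and the benefit may be out of reach. The SAP is dated April 2025 and written in the past tense. If the models have been run, a later covariate cannot add power to the governing test. The primary mania and depression analyses test group-by-week slopes, with a group term that takes up a starting difference. And if the endpoint measures are percent reductions or CGI-Improvement ratings, baseline is already largely built in. All of this stands. It limits the size and timing of the benefit, but it does not remove the case for reporting an adjusted analysis.

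A reader might infer more than the documents support:
- *That the group-only test is invalid or biased.* It is not, for the groups as randomised; its overall error is near 5%. The minimum-exposure rule for the analysis set is a separate matter, and baseline adjustment would not fully cure it.
- *That a 0.3 SD imbalance by itself raises the error to 12%.* That figure averages over all imbalances of at least that size, with a cutoff and r = 0.7.
- *That imbalance arises because entry sets no P-YMRS or CDI minimum.* Entry does rest on the CBCL ("Current symptoms of emotional dysregulation as indicated by combined T-scores on the Child Behavior Checklist"), but chance imbalance in SD units occurs under any entry rule; the 24.5% uses only the arm size.
- *That the P-YMRS level of 15 in the withdrawal rule shows the endpoint is a cutoff.* It is not offered as an endpoint definition.

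**Conclusion.** The point holds as a modest improvement to a valid analysis of secondary outcomes. The omission is plain in the text and the covariates are in hand. Its size cannot be fixed from the documents, because the outcome definition, the baseline-endpoint correlation and the effect size are not given.

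Under the stated assumptions a material power gain needs both an absolute cutoff and at least a moderate correlation. At r = 0.3 the gain is marginal under either definition once size is matched or the arms are smaller. For a measure relative to baseline it is small, nil or slightly negative. Protection against a chance imbalance is likewise mainly a benefit for a cutoff outcome. If the analysis is already done, what remains is interpretive: showing whether a secondary result depends on baseline imbalance.

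**What to change.** - Add one matching baseline score as a continuous covariate to each endpoint logistic model: P-YMRS for mania, CDI for depression, or baseline CGI severity where the measure is CGI-based. Test study group by likelihood ratio.
- State for each endpoint measure whether it is an absolute cutoff or relative to baseline, since this decides whether adjustment helps.
- Report the adjusted effect as a standardised risk difference. Label any adjusted odds ratio as conditional and not comparable with the unadjusted one.
- If the models have not been run, pre-specify the covariate. If they have, say that the unadjusted result governs and label the adjusted one a post hoc sensitivity analysis.

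Cost: a few lines of SAP text and a re-run on collected data. Downsides: one extra parameter in a small model, adjusted type I error of about 5 to 6%, a wider SE for the log-odds ratio, and a possible loss of up to about 2 points of power if the outcome is relative to baseline or the correlation is weak.

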Families with children and adolescents with NVLD/ASD and emotional dysregulation can speak with their primary care doctor to obtain a prescription for medication to treat mood disorders or receive a referral to a specialist. Available medications for treating severe mood problems in children include atypical antipsychotic medications and mood stabilizers and in some cases antidepressants. The study doctor can discuss the risks and benefits of other treatments with potential participants and their parent/guardian prior to enrollment.

Describe how risks to subjects are minimized, for example, by using procedures which are consistent with sound research design and which do not unnecessarily expose subjects to risk or by using procedures already being performed on the subject for diagnostic or treatment purposes.

All efforts are made to minimize risks to subjects. The protocol is designed to ensure that safety measurements are completed prior to study drug treatment and that the subject's response to study drug is closely monitored. Previous studies by our research group confirm that these study treatments are safe for use in children at these doses. All procedures used in this study are consistent with sound research design and do not unnecessarily expose subjects to risk. Clear drop criteria will be employed, as described below.

We will be using secure Partners workstations to access Vidyo, a videoconferencing platform, in combination with Skills Based Routing (SBR), a patient management software, to conduct the weekly study visits. Both Vidyo and SBR are secure mediums. Partners Information Systems and MGH Health Information Services have already approved this technology for use.

Describe explicitly the methods for ensuring the safety of subjects. Provide objective criteria for removing a subject from the study, for example, objective criteria for worsening disease/lack of improvement and/or unacceptable adverse events. The inclusion of objective drop criteria is especially important in studies designed with placebo control groups.

Each week, a study clinician will record any adverse events.

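### The AE-count Poisson model names no time-on-treatment term, so if one arm stops sooner its AE ratio is pulled down and a true excess is diluted

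*SAP*

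**What the plan says.** The SAP (Statistical Methods) gives AEs one sentence: "Adverse events (AEs) were analyzed using a Poisson regression model for AE counts", with Fisher tests added for prevalence. It lists no covariates, unit of analysis or exposure variable for that model. In the same paragraph the efficacy models do carry time; they "predict the outcome measure of interest from the study group, study week (continuous), and the study group-by-study week interaction". The error rate is common to everything: "All analyses were two-tailed with an alpha level of 0.05".

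The analysis set is a modified intention-to-treat set in which "participants had to be exposed to the study medications for ?2 weeks". The sign was lost when the PDF was read; I take it as at least 2 weeks.

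In the protocol (Research Design and Methods), the 6-week trial with 30 children per arm is set up "to compare efficacy and tolerability of the natural treatments". On collection, "Each week, a study clinician will record any adverse events", and the tele-visit description places this recording at the weekly visits. On leaving early, "drop from the study will occur at clinician discretion for worsening of clinical course, non-compliance with treatment, or inability to tolerate study treatment". Drop is also possible for poor response, missed appointments and low compliance. No scheduled AE follow-up after drop is described. The Data and Safety Monitoring section offers pager access for AEs that arise between visits.

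**The concern.** A child who leaves at week 2 has two weekly visits at which an AE can be recorded; a completer has six. Both can be in the analysis set, so observation time can differ threefold between analysed children. Since intolerance is itself a ground for drop, time on study may depend on the outcome being compared.

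A Poisson model of counts without an exposure term estimates a ratio of totals, not of rates. If one treatment drives more children off study, they contribute fewer weeks and so fewer AEs, and the comparison moves in that treatment's favour. The Fisher tests of prevalence also depend on observation time. The SAP does not compare stopping between arms, so nothing else in the plan would reveal that a modest AE count came from short exposure. Tolerability is one of the two comparisons the protocol sets out to make.

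**Working it through.** **Inputs from the documents.** 30 per arm, 6 weeks, weekly AE recording, about 2 weeks' minimum exposure, two-sided alpha 0.05. The documents give no AE rate, stopping rate or power for AEs, so there is no figure of the plan's own to reproduce.

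**Assumptions, not in the documents.** 0.1 to 0.5 AEs per child-week; stoppers leave at weeks 2 to 4 (mean 3); 10% stop in one arm and 20% to 40% in the other.

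**Formula.** In a two-arm Poisson model with no offset, the estimated ratio is the ratio of mean counts. At a constant weekly rate:

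ratio without offset = true rate ratio × (mean weeks, arm A ÷ mean weeks, arm B)

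With log(weeks) as offset, the second factor cancels. Both closed forms agreed with fitted models on a test data set.

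**Mean weeks.** Mean weeks = 6 × (1 − p) + 3 × p for stopping proportion p: 10% gives 5.7, 20% gives 5.4, 30% gives 5.1, 40% gives 4.8.

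**Equal true weekly rates.** Rejection rates are simulated at 0.5 AEs per child-week:

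| Stopping, A vs B | Ratio without offset | Rejection without offset |
|---|---|---|
| 20% vs 10% | 5.4/5.7 = 0.95 | about 8% |
| 30% vs 10% | 5.1/5.7 = 0.89 | 12–13% |
| 40% vs 10% | 4.8/5.7 = 0.84 | 20–21% |

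With the offset, the last two rows return to about 1.00, with rejection of 4.4% and 4.9%.

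**Lower AE rates.** The ratio is unchanged, but the test is less affected. For 40% vs 10%, rejection is about 12% at 0.25 per child-week and about 7% at 0.1. For 20% vs 10% at 0.1, expected totals are 30 × 0.1 × 5.4 = 16.2 and 30 × 0.1 × 5.7 = 17.1. The standard error of the log ratio is √(1/16.2 + 1/17.1) = 0.35, and the bias is log(0.947) = −0.054, or 0.16 standard errors. That leaves rejection at about 5%.

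**Equal stopping.** At 20% in each arm (week 3, 0.5 per child-week) the ratio is 1.00 with or without the offset. Rejection is 6.6% without and 4.9% with it, because chance variation in exposure adds variance that the model without an offset ignores.

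**A true excess.** With a true ratio of 1.25 in the arm with 40% stopping, the model without an offset estimates 1.25 × 4.8/5.7 = 1.05. At 0.5 AEs per child-week, power is about 8%, against about 30% with the offset.

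**AEs clustered early.** Take equal true rates, 40% vs 10% stopping and 3 AEs per completer.
- Weeks 1–2 at 3 times the later rate: weekly means are 0.9, 0.9, then 0.3. A stopper averages 2.1 AEs. Arm means are 0.6 × 3 + 0.4 × 2.1 = 2.64 and 0.9 × 3 + 0.1 × 2.1 = 2.91. The ratio is 0.91 without the offset and 0.91 × 5.7/4.8 = 1.08 with it; rejection is about 10% and 8%.
- Weeks 1–2 at 6 times the later rate: the ratio is 0.94 without and 1.12 with the offset; rejection is about 7% and 12–13%. Here the plain offset does worse.

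**Prevalence.** At a constant 0.1 per child-week, the chance of any AE is 1 − exp(−0.6) = 45% for a completer and 1 − exp(−0.3) = 26% for a child who leaves at week 3. The Fisher test is therefore not free of the problem.

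**The case against.** Four points on the other side have force.

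First, the SAP is silent, not prohibitive. A reader might infer that it specifies raw totals per child. It does not say so, and an offset may be in the analysis code. What stands is that the sentence, followed literally, yields a comparison of totals, in a paragraph that does name time for the efficacy models.

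Second, a reader might take it as stated that AE collection ends at drop. That is an inference from weekly visits being the only scheduled route. Pager access could capture some later AEs, but it is not scheduled follow-up.

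Third, the effect is conditional and may be small. It needs unequal stopping, and the protocol expects few AEs (Background and Significance; Foreseeable Risks and Discomforts). With rare AEs or a narrow gap in stopping, the false-positive rate stays close to 5%. This limits the effect on the test; the bias in the estimate does not shrink with the AE rate.

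Fourth, a plain offset assumes a constant weekly rate. If AEs cluster in the first two weeks it overcorrects and can do worse than no offset. This stands, and it means the offset should not be the only analysis.

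**Conclusion.** The concern holds as a gap in the written plan: exposure is not addressed for AE counts, although the design allows analysed children to be observed for about 2 to 6 weeks and makes intolerance a reason to leave. Under a constant weekly rate the direction is fixed: the ratio is pulled down for whichever arm stops sooner. Under the assumptions shown, the ratio falls to about 0.95 to 0.84 when the truth is 1.00. False-positive rates range from close to nominal, with rare AEs and a small gap, to about 21%.

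A stronger reading would be that the arm whose children stop sooner will look better tolerated than the other. The documents do not support that. They give no stopping rates by arm. Where that arm has a true excess, the usual result is dilution: 1.25 shown as 1.05 still points the right way, though with little power. The arm looks better than its weekly rate warrants, not necessarily better than its comparator.

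This affects a stated tolerability comparison, not the primary efficacy analysis. It is a cheap improvement.

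**What to change.** State in the SAP that the AE-count Poisson model uses log(weeks observed) as an offset, and report the result as an AE rate ratio per child-week. If the code already does this, one sentence settles the point; otherwise the model needs re-running.

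Add a sensitivity analysis of weekly AE counts with a study-week term, so that the conclusion does not rest on a constant rate.

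Beside the Fisher tests, tabulate by arm the weeks on treatment, all-cause stopping and stopping for intolerance.

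The cost is one offset term, one additional model and one small table. AEs are recorded weekly, so no new collection should be needed. The documents do not say that drop reasons are held as coded data, so the intolerance row may require a look at source records. The remaining downside is that the main rate ratio still assumes a roughly constant weekly rate.

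### The AE-count comparison rests on a plain Poisson model with no counting rule and no allowance for overdispersion, so its p-value is too small if children's counts vary more than Poisson

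*SAP*

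**What the plan says.** The plan for AEs is a single sentence in the SAP, Statistical Methods: "Adverse events (AEs) were analyzed using a Poisson regression model for AE counts", together with Fisher's "exact tests for AE prevalence". The general rule is "All analyses were two-tailed with an alpha level of 0.05". The sentence does not say whether the count is a total per child, a count per child-week or a count of AE entries. It does not say how a persisting AE is handled, and it names no robust variance, dispersion parameter or negative binomial alternative.

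In the same paragraph the mania, depression, autism-symptom and executive-function measures "were analyzed using mixed-effects Poisson regression models", so a within-child term is named there.

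The protocol (Research Design and Methods) gives the setting. On duration: "This will be a 6-week, open-label, randomized clinical trial study". On size: "We will enroll 60 subjects to allow for the randomization of 30 subject into each treatment arm". On collection: "Each week, a study clinician will record any adverse events", and the weekly tele-visit paragraph has the clinician "record any side effects or adverse events". Tolerability is named beside efficacy as something the trial compares.

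**The concern.** With its default standard error, a Poisson model of AE counts by arm uses only the total number of events in each arm. Five AEs in one child carry the same weight of evidence as one AE in each of five children. That is right only if events occur independently, so that a child's count has variance equal to its mean.

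Two things could break this here. Children aged 5 to 17, dosed by age or weight in part and allowed to continue other treatment, may differ in how readily they have or report AEs. And complaints of the kind listed under Foreseeable Risks and Discomforts, such as stomach upset, could persist from one weekly visit to the next and be counted each time, since no rule prevents it.

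If either happens, chance alone can make one regimen look better tolerated more often than the stated 5%. An exposure offset, which is a separate matter, would remove only the spread due to unequal time on treatment.

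**Working it through.** **Inputs from the documents.** Two-sided alpha 0.05 (SAP, Statistical Methods); 30 children per arm, weekly AE recording and 6 weeks of treatment (Protocol, Research Design and Methods).

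**Assumed inputs.** The documents give no AE rate, duration or dispersion. Let φ be the variance/mean ratio of the per-child count; it is varied below.

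**Step 1: formula.** With arm event totals E1 and E2, the model-based standard error of the log rate ratio is √(1/E1 + 1/E2). The true standard error is about √φ times that. The nominal 0.05 test therefore rejects a true null with probability 2 × [1 − Φ(1.96/√φ)].

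**Step 2: the plan's own figure.** At φ = 1 this is 2 × [1 − Φ(1.96)] = 0.050, the stated alpha. Simulation (40,000 trials per setting, 25 or 30 per arm, mean 1, 2 or 4 AEs per child) gave 0.048 to 0.051.

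**Step 3: other values of φ.** The simulated counts are gamma-Poisson.

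| φ (assumed) | 1.96/√φ | Type I error | Simulated, plain Poisson |
|---|---|---|---|
| 0.8 | 2.19 | 0.028 | not run |
| 1.25 | 1.75 | 0.080 | not run |
| 1.5 | 1.60 | 0.110 | 0.102–0.109 |
| 2 | 1.39 | 0.166 | 0.156–0.162 |
| 3 | 1.13 | 0.258 | 0.249–0.256 |

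Put another way, a reported p of 0.02 (z = 2.326) would become 0.058, 0.100 and 0.179 at φ = 1.5, 2 and 3.

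**Step 4: what could produce such values.**
- *Differences between children.* For gamma-Poisson counts, φ = 1 + mean × CV², where CV is the between-child coefficient of variation of the AE rate. With CV = 0.5, a mean of 1 AE gives 1 + 1 × 0.25 = 1.25, and a mean of 2 gives 1 + 2 × 0.25 = 1.5. Reaching φ = 3 at a mean of 1 needs CV² = 2.
- *Recounting.* If AEs start as a Poisson process and each is counted in k consecutive weeks, φ = E[k²]/E[k]. For k uniform on 1–2 weeks this is 2.5/1.5 = 1.67, and on 1–3 weeks 4.67/2 = 2.33. If every AE is counted once, k = 1 and φ = 1. This ignores cut-off at week 6.

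**Step 5: does one total per child solve it?** No. In an illustrative data set of 60 children over 6 weeks, generated with strong differences between children (weekly mean 0.3, CV² = 2), the Poisson standard error was 0.229 whether fitted to child totals or to child-weeks. The child-clustered value was 0.446. These figures show the mechanism and do not predict this trial.

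**Step 6: after the repair.** In the Step 2 and 3 simulations, type I error was 0.046–0.051 with a quasi-Poisson scale and 0.047–0.067 with robust standard errors, highest at φ = 3 and a mean of 1. A separate set of simulations put the robust test at up to 0.069.

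**The case against.** The strongest case against is that the documents do not show the problem occurring. Three stronger readings are tempting, and none is supported.

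- *Each weekly entry is counted as a new event.* The protocol says when AEs are recorded, not how they are counted. The SAP leaves the unit open, so double counting is possible but not stated.
- *The p-value will be too small.* At φ = 1 the test is valid, and below 1 it is conservative. The protocol's only hints, in Background and Significance and in Foreseeable Risks and Discomforts, are that AEs are few. With a low mean, differences between children keep φ near 1.
- *The tolerability comparison as a whole is unsound.* Fisher's tests on children with or without an AE are untouched by overdispersion or recounting.

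It is also fair that the SAP is a short methods paragraph that names no variance option for any model, so silence does not rule out robust errors. The hypothesis and main outcomes concern symptoms, and no decision rule uses the AE-count p-value.

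All of this limits the point without removing it. The paragraph names a within-child model for the rating scales and none for AEs, so a plain Poisson fit is the natural reading. The counting rule is missing on any reading.

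**Conclusion.** The point holds conditionally. As written, the AE count cannot be reproduced from the plan, and its test is anti-conservative if per-child counts are overdispersed. The type I error runs from 0.05 with no overdispersion to about 0.26 at a variance/mean ratio of 3. Where this trial falls in that range cannot be told from the documents, because every ratio used is an assumption. The calculation also assumes a model with arm as the only term, its default standard error, and about 25 to 30 children per arm. The consequence is confined to one of the planned AE analyses, but that analysis serves a comparison the protocol names as a purpose, so the sentence should be changed.

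**What to change.** In the AE sentence of the SAP, Statistical Methods:

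1. Define the outcome as one count per child of distinct AEs, with an AE that continues across weekly visits counted once, at onset.
2. Fit the Poisson model with robust (sandwich) or quasi-Poisson standard errors.
3. Report the estimated dispersion beside the rate ratio and its interval.

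The first item removes recounting, and the second covers differences between children; neither replaces the other. The cost is a sentence, a software option and the work of linking repeated weekly entries of the same complaint. No further data need be collected from families. If dispersion is near 1, the result will hardly change. If it is higher, the interval will be wider, and the robust test keeps the slight small-sample excess shown above. The SAP is written in the past tense, so if the analysis has already been run, the same change applies as a re-analysis.
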